1.5 Study relevance and expected impact

A growing body of evidence indicates that PCSK9 inhibitors result in profound reductions in blood levels of LDL-C, with an efficacy that is more potent and incremental to the effect of high-dose statin regimens - the current paradigm for management of dyslipidemia and for prevention of CAD anatomic and clinical progression. The present analysis, utilizing a multimodality approach of intracoronary imaging, aims to uniquely investigate the effect of PCSK9 inhibition on important aspects of coronary plaque burden, morphology and composition in humans including lipid content, inflammation, and fibrous cap thickness in the two non-infarct related arteries of patients with acute myocardial infarction. These morphological characteristics have been related to plaque vulnerability and rupture in pathological studies and, prospectively, with future cardiac events. The proposed study thereby aims to provide further insights on the effects of highly potent LDL-C reduction on atheroma progression, composition and microstructural plaque characteristics in a background of evidence of the efficacy of PCSK9 inhibitors in reducing LDL-C levels and of ongoing analyses assessing possible translation of this potent lipid-lowering potential into improved clinical outcomes. Considering the alarmingly high residual risk of anatomic and clinical progression of coronary atherosclerosis in a substantial proportion of patients treated with intensive statin regimens, the proposed study aims to assess the incremental efficacy of a novel, innovative treatment strategy in favorably affecting both plaque progression and plaque composition in a high-risk populations of patients who already experienced myocardial infarction and who derive the greatest benefit from aggressive lipid-lowering and other anti-atherosclerotic medications.

Acute myocardial infarction causes a systemic inflammatory reaction, which promotes inflammation and thereby induces plaque growth at non-culprit lesion sites as demonstrated in preclinical models. In addition, patients with myocardial infarction are known to harbor more vulnerable plaques in their non-infarct related arteries compared to stable CAD patients, thereby indicating an ideal population to study the PCSK9-mediated effects on atherosclerosis. As an additional feature, a multi-vessel assessment will be obtained in the proposed study, as plaque progression in the entire coronary artery tree is of greater interest compared to assessment of only a single selected arterial segment. Cardiovascular events are not limited to one single vessel segment and in this study we will focus specifically on selecting the clinically most relevant vessel regions, that is, according to previous pathology studies,^{8,43} the proximal portions of the major coronary arteries where most rupture-prone TCFAs are located and where the consequences of a myocardial infarction are highest based on the large amount of myocardium at risk.

2. STUDY OBJECTIVES

2.1 Primary objective

• To evaluate the effect of LDL-C lowering by means of the PCSK9 inhibitor alirocumab as compared with placebo on the change in percent atheroma volume (PAV) in non-infarct-related coronary arteries of patients who present with acute myocardial infarction, undergo percutaneous coronary intervention (PCI) in the infarct-related artery, and receive guideline-recommended high-intensity statin therapy.

2.2 Secondary objectives (please see also Appendix 1 to protocol)

- To evaluate the effect of the PCSK9 inhibitor alirocumab on the change in lipid core burden index (defined by NIRS), macrophage accumulation, and fibrous cap thickness of coronary plaques (defined by OCT) as compared with placebo in the non-infarct-related coronary arteries.
- To assess the effect of alirocumab on change in lipid levels (cholesterol, LDL-C, HDL-C, Lp(a), triglycerides, non-HDL-C, Apo B, Apo A-1, ratio Apo B/Apo A-1, Apo C-III), inflammatory biomarkers (hs-CRP, TNFa, IL-1b, IL-6, MPO, cystatine, SIRT1, SIRT6) and other selected biomarkers (hs-troponin T, NT-pro-BNP) and explore possible associations with changes in coronary plaque characteristics.

2.3 Safety objective

• To evaluate adverse events in patients treated with alirocumab.

3. RESEARCH PLAN

3.1 Study Design

This is a prospective, randomized, superiority, double-blind (assessor and patients blinded to treatment), placebo-controlled, parallel-group, multi-center study to evaluate the effect of alirocumab on coronary atherosclerotic plaque burden and composition as assessed by multi-modality intracoronary imaging at baseline and following 52 weeks of treatment in patients presenting with acute myocardial infarction undergoing PCI. The primary endpoint will be assessed at 52 weeks post randomization.

3.2. Number of patients

A total of 294 patients will be randomized in a 1:1 ratio to either alirocumab or placebo. Patients will be screened for eligibility based on anatomic criteria (number of arteries without significant obstructive atherosclerotic disease), estimated suitability for intracoronary imaging of 2 non-infarct-related coronary arteries, clinical and LDL-C level inclusion criteria as detailed in **section 4**. Justification of the sample size is described in: .

Please see Appendix 1 to Protocol for adjusted sample size

3.3 Number of centers

The study will be conducted at 9 centers in Switzerland (5), Austria (1), Netherlands (2), Denmark (1).

3.4 Expected study duration

After signing the consent form, patients will be enrolled in the study. Following screening, enrollment and randomization (Day 1), the total study duration for each individual patient will amount to 52 weeks consisting of:

- A 52-week treatment period (Week $0 \rightarrow$ Week 52) with planned follow-up and study interventions;
- The final study visit should take place at week 52 (-0/ + 14). An additional injection of the IP at week 52 shall take place to assure that the final follow-up is performed within 14 days after the last injection.

The end of the study will be defined as the date when the last randomized patient completes the week 52 end-of-study (EOS) assessment.

3.5 Interim safety analysis

Interim safety analyses will be conducted based on the reported frequency of SAE and AESI by the DSMB. The timing and frequency of these analyses will be determined by the members of the DSMB (at least one).

4. PATIENT ELIGIBILITY

4.1 Inclusion Criteria

- Male or female, age ≥ 18 years at screening
- Acute myocardial infarction: acute ST-segment elevation myocardial infarction (STEMI) with pain onset within ≤24h, or non-ST segment elevation myocardial infarction (NSTEMI), with at least one coronary segment (culprit lesion) requiring PCI
- LDL-C ≥70 mg/dL (≥1.8 mmol/L) assessed prior to, or during PCI in patients who have been receiving any stable statin regimen within ≥ 4 weeks prior to enrollment; OR LDL-C ≥125 mg/dL (≥3.2 mmol/L) in patients who are statin-naïve or have not been on stable statin regimen for ≥ 4 weeks prior to enrollment
- At least two major native coronary arteries ("target vessels") each meeting the following criteria for intracoronary imaging immediately following the qualifying PCI procedure:
 - Angiographic evidence of <50% reduction in lumen diameter by angiographic visual estimation
 - Target vessel deemed to be accessible to imaging catheters and suitable for intracoronary imaging in the proximal (50mm) segment ("target segment")
 - Target vessel may not be a bypass (saphenous vein or arterial) graft or a bypassed native vessel
 - Target vessel must not have undergone previous PCI within the target segment
 - Target vessel is not candidate for intervention at the time of qualifying PCI or over the following 6 months in the judgment of the Investigator
- Hemodynamic stability allowing the repetitive administration of nitroglycerine
- Ability to understand the requirements of the study and to provide informed consent
- Willingness to undergo follow-up intracoronary imaging

4.2 Exclusion Criteria

- Left-main disease, defined as ≥50% reduction in lumen diameter of the left main coronary artery by angiographic visual estimation
- Three-vessel disease, defined as ≥70% reduction in lumen diameter of three major epicardial coronary arteries by angiographic visual estimation or in major branches of one or more of these arteries, irrespective of the localization (proximal 50mm or more distal localization) of the obstructive lesions
- History of coronary artery bypass surgery
- TIMI flow <2 of the infarct-related artery after PCI
- Unstable clinical status (hemodynamic or electrical instability)
- Significant coronary calcification or tortuosity deemed to preclude IVUS, NIRS and OCT evaluation
- Uncontrolled cardiac arrhythmia, defined as recurrent and symptomatic ventricular tachycardia or atrial fibrillation with rapid ventricular response not controlled by medications in the past 3 months prior to screening
- Severe renal dysfunction, defined by estimated glomerular filtration rate <30 ml/min/1.73m²
- Active liver disease or hepatic dysfunction.
- Known intolerance to rosuvastatin OR Known statin intolerance defined by the following criteria: inability to tolerate at least 2 different statins (one statin at the lowest starting average daily dose and the other statin at any dose); intolerance associated with confirmed, intolerable statin-related adverse effect(s) or significant biomarker abnormalities; symptom or biomarker changes resolution or significant improvement upon dose decrease or discontinuation; and symptoms or biomarker changes not attributable to established predispositions such as drug-drug interactions and recognized conditions increasing the risk of statin intolerance
- Known allergy to contrast medium, heparin, aspirin, ticagrelor or prasugrel
- Known sensitivity to any substances to be administered, including known statin intolerance
- Patients who previously received alirocumab or other PCSK9 inhibitor
- Patient who received cholesterol ester transfer protein inhibitors in the past 12 months prior to screening
- Treatment with systemic steroids or systemic cyclosporine in the past 3 months
- Known active infection or major hematologic, metabolic, or endocrine dysfunction in the judgment of the Investigator
- Planned surgery within 12 months
- Patients who will not be available for study-required visits in the judgment of the Investigator
- Current enrollment in another investigational device or drug study
- History of cancer within the past 5 years, except for adequately treated basal cell skin cancer, squamous cell skin cancer, or in situ cervical cancer
- Estimated life expectancy less than 1 year
- Female of childbearing potential (age <50 years and last menstruation within the last 12 months), who did not undergo tubal ligation, ovariectomy or hysterectomy

4.3. Emergency unblinding procedure

In case of a medical reason for emergency unblinding, the investigator will contact the pharmacist on call at the Bern University Hospital. The unblinding procedure will be activated upon reception of a corresponding form per Fax (Number [contact]) from the requesting investigator. The pharmacist has access to the randomization list linking the patient's study number with the randomly allocated treatment.

4.4 Justification of LDL-C criteria for eligibility

The rationale for the LDL-C eligibility thresholds in conjunction with pre-enrollment statin treatment status is in line with previous studies with PCSK9 inhibitors, also accounting for specific patient selection criteria uniquely applicable in the present study. In previous studies, PCSK9 inhibitors were administered either instead of a statin (e.g. due to statin intolerance) or on top of maximum tolerated statin therapy if LDL-C levels were above target levels as determined by individual patient cardiovascular risk. In those previous PCSK9 studies, a lipid-stabilizing period was applied and PCSK9 inhibitor treatment was initiated if LDL-C levels remained above targets despite maximally tolerated statin therapy with or without other lipid-modifying agents. In contrast, in the present study a lipid-stabilizing phase is not feasible as a result of the enrolment of patients in the acute setting of myocardial infarction, and due to the performance of the baseline intracoronary imaging evaluation (a prerequisite to proceed to randomization) during the clinically indicated cardiac catheterization in the acute clinical setting. This study will therefore require that patients either have LDL-C levels at screening above the guideline-recommended target of 70 mg/dL (1.8 mmol/L)^{44,45} while on prior stable statin treatment, or are on no prior statin treatment and have LDL-C levels ≥125 mg/dL (≥3.2 mmol/L). The latter approach accounts for the fact that, in patients with LDL-C levels ≥ 125 mg/dl (3.2 mmol) without concurrent treatment, LDL-C levels would still remain above target despite an estimated mean 43% reduction reportedly achievable with rosuvastatin 20mg (protocol-mandated background statin therapy throughout the study period for both treatment arms). Although a lipidstabilizing phase is not feasible in the present study, the advantage of the present approach will be the possibility to uniquely investigate changes in coronary atheroma burden and composition in response to PCSK9 inhibitor treatment in high-risk patients in the acute phase of myocardial infarction who are expected to derive maximal benefit from the treatment (as suggested by earlier studies with statins).

5. PATIENT SELECTION AND ENROLLMENT

5.1 PATIENT SCREENING

Patients undergoing clinically indicated PCI for acute myocardial infarction (STEMI or NSTEMI) will be screened for clinical and anatomic eligibility for study participation. STEMI will be defined by symptom onset within 24 hours and ST-segment elevation of ≥ 1 mm in 2 or more contiguous leads, true posterior MI, or new left bundle branch block. NSTEMI will be defined as chest pain >30 min and rise of troponin. Study enrollment will require evidence of two major, non-infarct-related coronary arteries (defined as "target vessels" for the purpose of intracoronary imaging) without significant lesions in their proximal (50mm) segments (significant lesions defined as >50% reduction in lumen diameter by angiographic visual estimation). Patients will either need to be on any stable statin treatment for ≥ 4 weeks prior to study enrollment and have an LDL-C value of ≥ 70 mg/dL (1.8 mmol/L) determined prior to, or during PCI, OR have an LDL-C value of ≥ 125 mg/dL (3.2 mmol/L) if they are stain-naïve or have not been on a stable (≥ 4 weeks) statin regimen. Among patients considered to be potential study candidates based on all other inclusion and exclusion criteria, LDL-C levels will be measured rapidly from blood samples drawn after the diagnostic angiography and before completion of the qualifying PCI. For this purpose, a validated, point-of-care assay available at each participating study center will be used for prompt measurement of LDL-C levels to determine eligibility for enrollment.

5.2 Patient enrollment

Patient who fulfil all inclusion criteria (including LDL-C levels), do not meet any of the exclusion criteria, and sign the informed consent form will be considered enrolled and will undergo intracoronary imaging. All patients will be specifically asked if they consent to inclusion of their blood samples in the biobank. Patients who do not meet all inclusion criteria or meet any exclusion criteria will be considered screen failures and cannot be rescreened. Due to the particular situation of patients suffering from a heart attack with STEMI and the emergency need for treatment, a specific informed consent process will be applied (see also under 13.3 "Patient information and informed consent"):

- If the patient is conscious and in a position to take an informed decision, he/she will be asked for consent prior to the randomization.
- If the patient is conscious but, according to the treating cardiologist, not in position to read, interpret and sign the informed consent form, an oral consent will be asked for and documented in the informed consent form. As soon as possible after the intervention, the patient will be asked to confirm his/her decision by signing the informed consent form.
- Unconscious patients will not be included in the study.

Eligible patients will be considered enrolled once the consenting form has been signed and they will subsequently receive a unique Secutrial identifier, assigned by a web-based database system. The identifier will remain constant throughout the entire clinical study. Additionally, a blinded randomization identifier will be assigned when the patient is randomized. Randomization of enrolled patients will be performed only in patients with successful 2-vessel intracoronary imaging (or exceptionally also two regions of interest in the same vessel, e.g. in case of minimal caliber of one of the two non-infarct related vessels two ROI may be obtained in the larger non-infarct related vessel.), defined as successful imaging of the 2 imaging target vessels, at minimum by means of IVUS (modality used for the study's primary endpoint). Intracoronary imaging will be performed as deemed clinically feasible and safe by treating operators, aiming at successful imaging but without compromising patient safety according to physician's judgment. Imaging will be performed preferably immediately after PCI and latest within 24 hours after PCI. A screening log of all enrolled patients who undergo (successful or unsuccessful) intracoronary imaging will be maintained on the database A total of 220 enrolled patients will be randomized. Justification of the sample size calculation is described in Section 13.1.

5.3 Randomization

Randomization will be performed once eligibility is confirmed (after all inclusion and exclusion criteria have been checked), written informed consent has been obtained, and after a successful baseline imaging procedure including at minimum successful IVUS of the 2 identified target vessels. For better balance, randomization will be stratified for study center; use of stable (\geq 4-week) statin treatment at presentation; and STEMI vs. NSTEMI. Randomization will be done in a double-blind fashion with 1:1 allocation. Allocation sequences will be based on computer-generated random numbers. These sequences will be generated by an independent statistician and concealed using a central randomization system. To ensure a balanced allocation of treatment and control over time, randomization lists will be generated in blocks of 2, 4, or 6 patients and to enforce concealment, block size will be generated at random. Each patient will receive one randomization number and each randomization number will be assigned to a single patient. The randomization number will be indicated on the case report form.

Each patient will be allocated to one of the following treatments in a double blind fashion:

- Alirocumab 150 mg Q2W SC at 1.0 ml via an autoinjector
- Placebo Q2W SC at 1.0 ml via an autoinjector

Treatment with the investigational product (IP) (alirocumab or placebo) will start on Day 1 (Week 0) and finish on Week 50. This treatment will be on top of evidence-based optimal medical treatment, including rosuvastatin 20mg/day throughout the entire study period of 52 weeks (described in detail in **section 6.2**).

A patient is considered randomized once randomization to IP (alirocumab or placebo) is completed. Once randomized, the patient is included in the intention-to-treat (ITT) population. Study visits will occur at day 1 (randomization), Week 2, 4, 8, 12, 24, 48, 52 and 56 (section 8.1).

Every effort will be made that treatment assignment is un-blinded only when knowledge of the treatment is judged to be essential for patient safety. Unblinding for other reasons will be considered a protocol violation. The steering committee will be informed before any unblinding procedure is effective.

6. TREATMENT INTERVENTIONS

6.1 Investigational products

Investigational products in this study include alirocumab and placebo.

6.1.1 Composition and storage

Alirocumab will be administered as a sterile solution in a single-use, disposable, prefilled autoinjector pen for fixed-dose subcutaneous injection. The prefilled pen contains 1.0 ml volume of 150mg alirocumab in histidine, pH 6.0, polysorbate 20, and sucrose. The dosage is in keeping with phase-3 studies with alirocumab.²⁹ Placebo will be prepared in the same formulation as alirocumab without the addition of protein and will be administered in an identical prefilled pen containing 1.0 ml of deliverable volume. Both preparations will be manufactured and packaged by Sanofi / Regeneron, and will be stored refrigerated and protected from light.

Detailed information regarding storage will be contained in an IP manual that will be sent to each participating center. Investigators or other authorized persons (e.g., pharmacists) are responsible for storing the IP in a secure and safe place in accordance with local regulations, labeling specifications, policies, and procedures. Control of storage conditions, especially control of temperature (refrigerated storage) and information on in-use stability should be managed according to the rules provided by the product manufacturer. The product will be stored at the investigational site in an appropriate locked room, under the responsibility of the Investigator, and kept in a refrigerator between +2°C and +8°C (36°F to 46°F) at the site. The temperature of the site refrigerator should be checked daily and recorded on a log sheet.

6.1.2 Route and method of administration

A prefilled pen training guide (auto-injector training guide) will be provided to the sites and instructions for use (auto-injector for use) will be provided to the patient. The IP will be kept outside the refrigerator at room temperature for about 30 to 40 minutes immediately prior to administration. Each administration will consist of 1.0 mL SC injection in the abdomen, thigh, or outer area of upper arm (deltoid region). If another concomitant drug is being injected the patient should be advised to use

different injection sites. The used prefilled pens will be discarded in a sharp container which will be provided to patients.

6.1.3 Timing of administration

IP administration will be will be performed between Day 1/Week 0 and Week 50. IP administration will be initiated on Day 1/Week 0 during hospitalization for the index event, and will next be performed at planned visits at Week 2 and Week 4 at the Investigator site by qualified staff member. During these visits, patients will be trained for self-administration and noted in the injection diary distributed during the first visit (day 1). As the injection are scheduled to take place on visits including blood withdrawal, the IP will be administered after the blood sampling has been completed.

Following Week 4 (i.e., starting at Week 6), the IP will be self-administered at home once every 2 weeks up to Week 52 in accordance with instructions previously given to patients and noted in the injection diary. The IP may also be administered by another designated person (such as a spouse, relative, etc.). In this case, it must be ensured that this person has been adequately trained by the study staff prior to administering the injection. For patients or designated persons who do not feel comfortable to proceed to self-administration after Week 4, the IP may be administered on the investigational site at Weeks 6 and 8 (or later, if the patient wished so) with continuing patient training. In exceptional cases, if a patient prefers to have the injection performed at the study site and provisions are able to be made to accommodate the administration of injections at the site, it may also be allowed.

It is acceptable to have a window period of ± 3 days for IP administration. If an injection is delayed by more than 7 days from the planned date, then the patient should return to the original schedule of administration without administering delayed injections. If a planned injection is delayed by less than or equal to 7 days, then the patient should administer the delayed injection and then resume the original schedule of alirocumab administration. Patients who completely miss a scheduled dose of the IP will be instructed to continue and administered the next dose as scheduled. Consecutive injections should not be administered within less than 7 calendar days.

Each patient will receive a diary to record the injections. The diary will be prepared by the study nurse and handed out to the patient during the visit at week 4. The patient will be asked to record each injection and asked to bring the diary with her/him for each visit.

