7. STUDY PROCEDURES

7.1 Randomization visit (Day 1 / Week 0)

Patients who fulfill all inclusion criteria, meet none of the exclusion criteria, and provide signed informed consent will be enrolled in the study and undergo 2-vessel intracoronary imaging within 24 hours after completion of the clinically indicated PCI. Whenever clinically reasonable, the imaging procedure shall be performed immediately after PCI. If the treating physician prefers a staged imaging procedure (e.g. due to patient discomfort), the procedure may be performed within 24 hours after PCI. Patients with successful intracoronary imaging (defined as at minimum successful IVUS of 2 target vessels) will next undergo randomization (section 5.3).

The initial diagnostic procedure and PCI procedure will be performed by the usual clinical team in the catheterization laboratory by current standards and institutional protocols. Data that will be recorded at baseline include clinical and demographic data, use of medications, 12-lead ECG, angiographic data, IVUS, NIRS, and OCT pullback. Baseline laboratory values will be measured in local labs at each participating center and will include hematocrit, hemoglobin, lipid values (total cholesterol, LDL-C, HDL-C, triglycerides), glucose, liver panel (ALT, AST ALP, total bilirubin) and CK levels. A blood sample for rapid determination of LDL-C levels (study inclusion criterion) will be drawn among potential study candidates ("baseline blood draw #1"). If eligibility with respect to LDL-C levels is confirmed and the patient is enrolled in the study (section 4.1), a subsequent blood draw ("baseline blood draw #2") will be made for measurement for all other variables listed above at the local lab of the participating center. During the same blood draw, samples will be obtained that will be transferred to a dedicated biobank for specific subsequent measurements as detailed in section 9.3.2. To avoid patient discomfort related to consecutive blood draws, blood samples for "blood draw #1 and #2" will be drawn from venous catheters that are placed in patients with acute myocardial infarction as per standard clinical practice; no consecutive puncture will be required for the purpose of serial blood draws.

The time frame between Week 0 (first administration of the IP) and Week 52 (last administration of the IP, follow-up intracoronary imaging) comprises the "treatment period" (**Figure 2**).

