7.6 Week 24 (clinical visit)

The following data will be obtained and procedures performed:

- Vital signs (blood pressure, heart rate)
- Record AEs / product complaints
- Record concomitant medications including statin treatment
- Reinforce dietary recommendations (adherence to ATP III TLC diet)
- Encourage patient to maintain stable physical activity level
- Check compliance by diary document ation and returned IMPs in container
- Dispensation of 12 IMPs, coolbox and container for used IMPs

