7.9 Week 52 (end-of-study clinical visit) +14 days*/ -0 days

The following data will be obtained and procedures performed:

- Patient admission, performance of follow-up intracoronary imaging (IVUS, NIRS, OCT)
- Vital signs (blood pressure, heart rate)
- Record AEs / cardiovascular events / product complaints
- Record concomitant medications including statin treatment
- Check compliance by diary documentation and returned IMPs in containerReinforce dietary recommendations (adherence to ATP III TLC diet)
- Encourage patient to maintain stable physical activity level
- Obtain fasting blood samples for the following measurements (to be performed at local investigation site lab):
 - Hematology: blood cell count including hematocrit, hemoglobin, RBC count, WBC count with differential count and platelets
 - Chemistry: plasma glucose, sodium, potassium, creatinine

- Liver panel (ALT, AST, ALP, and total bilirubin)
- CK
- Obtain fasting blood sample for the following measurements (samples to be transferred to biobank and measures to be performed centrally):
 - total-C, LDL-C (Friedewald equation), HDL-C, triglycerides, non-HDL-C,
 - measured LDL-C (beta quantification)
 - Apo B, Apo A-1, ratio Apo B/Apo A-1, Apo C-III, Lp(a)
 - hs-CRP, hs-TNT, NT-pro-BNP
 - Other biomarkers specified in section 9.3.2 (Table 2)

If a patient is not in fasting conditions, no blood sample will be collected and a new appointment will be given the day after or as close as possible to this date with instruction to be fasted.

* Should it is not be possible to schedule the final visit on week 52, a maximal delay of 14 days may be acceptable. In this case, an additional injection of the IP at week 52 shall take place to assure that the final follow-up is performed within 14 days after the last injection.

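### The protocol states the last injection inconsistently (Week 50, Week 52, or whichever the final visit requires), and the Week 50 text with a late final visit breaks the schedule's own two-week limit

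*Protocol*

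**What the plan says.** The protocol gives the time of the last injection in three ways.

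- **Week 50.** Section 5.3 says treatment "will start on Day 1 (Week 0) and finish on Week 50". The first sentence of 6.1.3 has administration "performed between Day 1/Week 0 and Week 50".
- **Week 52.** The second paragraph of 6.1.3 says "the IP will be self-administered at home once every 2 weeks up to Week 52". Section 7.1 describes "Week 52 (last administration of the IP, follow-up intracoronary imaging" as the end of the treatment period. Section 3.4 says "An additional injection of the IP at week 52 shall take place to assure" that follow-up falls within 14 days of the last injection, and spells out no condition.
- **Week 50 or 52, depending on the final visit.** The synopsis (dose regimen) ties the choice to the end-of-study visit. The 7.9 footnote covers a visit that cannot be held at Week 52: "In this case, an additional injection of the IP at week 52 shall take place".

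Three other provisions bear on this. The final visit may fall from Week 52 to 14 days later (3.4, 7.9). The study schedule requires that visit no more than two weeks after the last injection. Section 6.1.3 allows ±3 days for each injection and, at visits with both, puts blood sampling before the injection.

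On supply, injections are given on site at Weeks 0, 2 and 4. Twelve pens are handed out at Week 4 (7.3) and twelve more at Week 24 (7.6: "Dispensation of 12 IMPs, coolbox and container for used IMPs"). Compliance is checked from the diary and the returned pens (7.6, 7.9).

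**The concern.** Sites work from the operative sections, and these disagree; 6.1.3 disagrees with itself. No order of precedence is given. The contents list also still shows a different window for the final visit (+0/-7 days) from the body text (+14/-0), so the sections were not fully harmonised when the timing was changed.

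At stake is the time from last dose to the Week 52 blood sample. LDL-C and other lipid markers at Week 52 are secondary endpoints (9.2.2), and PCSK9 is among the planned biomarkers (8.3.2, Table 2). Biomarker levels are to be correlated with change in PAV (8.3.2), and LDL reduction over the study defines one of the stratified analyses of the primary endpoint (9.1). Placebo contains no protein (6.1.1), so an effect that depends on time since dose could arise only in the alirocumab arm. That last step is an inference; the protocol gives no time course.

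**Working it through.** **Inputs.** Week 50 = day 350; Week 52 = day 364. Final visit on days 364 to 378 (3.4, 7.9). Injection window ±3 days and blood before injection (6.1.3). Limit of 14 days from last injection to final visit (study schedule).

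**Formula.** Gap = day of blood sample minus day of the latest injection before it. No dose is skipped, and an injection on the visit day follows the blood draw.

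**The protocol's own limit.** Under the conditional rule with on-schedule doses:
- visit on day 364: 364 − 350 = 14 days
- visit on day 365: 365 − 364 = 1 day
- visit on day 378: 378 − 364 = 14 days

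The maximum is 14, so the two-week limit is reproduced. A Week 52 injection for everyone gives the same figures, because on day 364 the blood is drawn first and the gap still runs from Week 50.

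**Week 50 for everyone.**
- visit on day 364: 364 − 350 = 14 days
- visit on day 378: 378 − 350 = 28 days, twice the limit
- visit on day 378 with the Week 50 dose 3 days early: 378 − 347 = 31 days

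**Effect of the ±3-day window on the other two readings.** With the Week 50 dose 3 days early (day 347), the Week 52 dose 3 days late (day 367) and a visit on day 367 with blood first, the gap is 367 − 347 = 20 days. With the Week 52 dose 3 days early (day 361) and a visit on day 378, it is 378 − 361 = 17 days.

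| Last-injection rule | Doses on schedule | With ±3 days |
|---|---|---|
| Week 50 for all | 14 to 28 days | 11 to 31 days |
| Week 52 for all | 1 to 14 days | 1 to 20 days |
| Week 52 only if visit is late | 1 to 14 days | 1 to 20 days |

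Skipped doses, longer delays and visits rebooked because the patient was not fasting are not included and could lengthen the gap.

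**Pens.** Home doses from Week 6 to Week 52: (52 − 6)/2 + 1 = 24. To Week 50: (50 − 6)/2 + 1 = 23. Dispensed for home use: 12 + 12 = 24. With 3 on-site injections, supply is 27; dosing through Week 52 uses 27 and dosing through Week 50 uses 26. This takes the Week 4 on-site injection as separate from the 12 pens handed out that day, as the schedule lists them.

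**Week 4 for comparison.** Visits 2 and 3 each carry ±3 days, so the Week 4 sample falls 14 − 6 = 8 to 14 + 6 = 20 days after the second dose.

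**The case against.** The best reply is that the synopsis and the 7.9 footnote already hold the intended rule: Week 50 normally, Week 52 if the visit is late. The Week 52 sentence in 3.4 follows directly on the visit window, and its stated purpose needs the extra dose only for a late visit. Home dosing up to Week 52 in 6.1.3 can be read as an outer bound, and the 24th home pen is what a conditional dose requires. On this view 5.3 and 7.1 are loosely worded rather than rival regimens.

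That reading is plausible, but the text does not settle it. Section 5.3 and the opening of 6.1.3 state Week 50 with no exception, 7.1 names Week 52 as the last administration, and a site following 5.3 with a late visit breaks the schedule's limit.

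Other parts of the reply stand in full. Most of the remaining spread comes from the visit window: reconciling everything to the conditional rule would still leave 1 to 14 days. The affected measures are secondary, and no shift in LDL-C or PCSK9 can be calculated from the protocol.

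A reader might infer more than the text supports:
- **A single range of 0 to 17 days since dose.** This matches no reading. Zero needs an injection before the blood draw on the same day. Seventeen is the maximum only for a visit exactly at Week 52 after a Week 50 dose given 3 days early.
- **A fully adherent patient scored at 26/27 = 96%.** The protocol defines no adherence percentage or denominator, and the diary records each injection, so an unused pen need not count as a missed dose.
- **Week 4 as a fixed 14-day comparator.** The visit windows make it 8 to 20 days.

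**Conclusion.** The inconsistency is real, and one of the stated rules conflicts with another stated rule: Week 50 as the last dose and a visit at +14 days give 28 days since dose (31 with an early dose) against a limit of 14. The other readings meet the limit when doses are on schedule, though the ±3-day injection window alone can take them to 20 days. The expected number of returned pens is not single-valued either, since 27 are supplied and 26 or 27 are used.

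The consequence is that Week 52 lipid and PCSK9 values, their correlation with plaque change and the analysis stratified by LDL reduction could combine different times since last dose. The direction and size of any effect cannot be derived from the documents. It would be wrong to read this as a threat to the main result: the PAV comparison, its sample size, alpha and power do not use time since dose.

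This is a minor consistency correction. The figures assume visits inside the stated window, no skipped dose and blood drawn before any same-day injection. No view is taken on which last injection is right.

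**What to change.** 1. Reconcile the synopsis, 3.4, 5.3, 6.1.3, 7.1 and 7.9 to one statement of the last injection that agrees with the two-week limit in the study schedule. Which statement to adopt is for the sponsor.
2. Align the pens dispensed, and the number expected back, with that statement.
3. Make explicit that the blood-before-injection order in 6.1.3 also applies to any injection on the day of the Week 52 visit, including one given at home. Section 7.9 lists no injection among the visit procedures, so the order is not clearly covered now.
4. Record the date of the last injection with the Week 4 and Week 52 samples. Some variation in time since dose will remain after the wording is fixed, and this makes it visible.

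The cost is wording in six places and one data field, whose content is already in the injection diary. A table restricted to samples taken 11 to 17 days after dosing is not recommended. It selects on a post-randomisation variable, under the conditional rule it would drop visits at +1 to +10 days with on-schedule doses, and such detail belongs in the SAP.
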